EudraCT	European Clinical Trials Database
f	Breathing Frequency
FC	Flow Chart
FDA	Food and Drug Administration
FGF/R	Fibroblast Growth Factor/Receptor
FLT3	Fms-like Tyrosine Kinase-3
FVC	Forced Vital Capacity
GCP	Good Clinical Practice
Hgb	Hemoglobin
HR	Heart Rate
HRQoL	Health Related Quality of Life
HRCT	High Resolution Computed Tomography
IC	Inspiratory Capacity

ICH	International Council on Harmonization
IEC	Independent Ethics Committee
ILD	Interstitial Lung Disease
IPF	Idiopathic Pulmonary Fibrosis
IRB	Institutional Review Board
IRT	Interactive Response Technology
ISF	Investigator Site File
JRS	Japanese Respiratory Society
KBILD	King's Brief ILD Questionnaire
LDH	Lactic Acid Dehydrogenase
LPDD	Last Patient Drug Discontinuation
MAH	Marketing Authorization Holder
MedDRA	Medical Dictionary for Drug Regulatory Activities
NAC	N-Acetyl Cystine
nRTKs	Non-receptor Tyrosine Kinases
OPU	Operating Unit
PDGF/R	Platelet Derived Growth Factor/Receptor
PR	Pulmonary Rehabilitation
QLF	Quantitative Lung Fibrosis Score
QoL	Quality of Life
REML	Restricted Maximum Likelihood ²
RS	Randomized Set
RTKs	Receptor Tyrosine Kinases
SADR(s)	Serious Adverse Drug Reaction(s)
SAE	Serious Adverse Event
SaO ₂	Oxygen Saturation
SD	Standard Deviation
SOP(s)	Standard Operating Procedure(s)
SP _{O₂}	Blood Oxygen Saturation or peripheral capillary oxygen saturation
Te	Expiration Time
Ti	Inspiration Time
TLC	Total Lung Capacity
TSAP	Trial Statistical Analysis Plan
UCSD SOBQ	University of California San Diego Shortness of Breath Questionnaire
ULN	Upper Limit of Normal
US	United States
VE	Minute Ventilation
VEGF/R	Vascular Endothelial Growth Factor/Receptor
VCO ₂	Carbon Dioxide Production
VMU	Vector Magnitude Units per Minute
VO ₂	Oxygen Consumption
V _T	Tidal Volume
Wcap	Maximal Work Capacity
WHO	World Health Organization
WOCBP	Woman of childbearing potential
6MWD	Six Minute Walk Distance

6MWT

Six Minute Walk Test

1. INTRODUCTION

1.1 MEDICAL BACKGROUND

Idiopathic Pulmonary Fibrosis (IPF) is a chronic disease of unknown aetiology that is characterized by progressive fibrotic destruction of the lung, resulting in disabling dyspnea and poor gas exchange. The average life expectancy in IPF patients is 3-5 years ([U07-1248-07](#)). Nintedanib (OFEV) is a small molecule anti-fibrotic kinase inhibitor (PDGF/R [platelet derived growth factor/receptor], FGF/R [fibroblast growth factor/receptor], VEGF/R [vascular endothelial growth factor/receptor]) that has been developed for the treatment of IPF. Theoretical and pharmacological models suggest that inhibition of these kinase receptors may interfere with the fibrotic signaling cascade. OFEV was approved as a treatment for IPF in 2014.

1.2 DRUG PROFILE

Nintedanib is a small molecule that inhibits multiple receptor tyrosine kinases (RTKs) and non-receptor tyrosine kinases (nRTKs). Nintedanib inhibits the following RTKs: platelet-derived growth factor receptor (PDGFR) and fibroblast growth factor receptor (FGFR) 1-3, vascular endothelial growth factor receptor (VEGFR) 1-3, and Fms-like tyrosine kinase-3 (FLT3). Among them, FGFR, PDGFR, and VEGFR have been implicated in IPF pathogenesis. Nintedanib binds competitively to the adenosine triphosphate (ATP) binding pocket of these receptors and blocks the intracellular signaling which is crucial for the proliferation, migration, and transformation of fibroblasts representing essential mechanisms of the IPF pathology. In addition, nintedanib inhibits the following nRTKs: Lck, Lyn and Src kinases. The contribution of FLT3 and nRTK inhibition to IPF efficacy is unknown.

For a more detailed description of the nintedanib profile please refer to the current approved labeling ([R18-1289](#)).

1.3 RATIONALE FOR PERFORMING THE TRIAL

Pulmonary rehabilitation (PR) has been defined as an “evidence-based, multidisciplinary, and comprehensive intervention for patients with chronic respiratory disease who are symptomatic and often have decreased daily life activities.” (ATS/ERS Statement on Pulmonary Rehabilitation). ([R13-1578](#)) Data supporting its use come largely from the study of COPD (chronic obstructive pulmonary disease), in which PR has been shown to increase exercise endurance, decrease dyspnea, improve health related quality of life, and reduce health-care cost. Data examining the role of PR in interstitial lung disease (ILD) has been less voluminous and needs to be addressed. Studies that support the use of PR in ILD have all been too short and too small to draw any conclusions. Studies that have been completed use similar protocols to the COPD PR experience, with total PR time of 10 – 12 weeks. Most have included both an exercise and educational component. The recent PHYSACTO study utilized and additional component of behavioural modification and training as part of Jean

Bourbeau's "Living Well with COPD" program ([P16-04442](#)). Thus far there are no reported ILD programs that have included this component.

Studies that have been done with PR for ILD, have shown short term impact but no enduring effect in 6MWD, QoL and symptoms ([R18-1704](#)). One likely cause of this outcome is that the PR has a benefit, but once stopped the patient is left with an underlying progressive debilitating disease that cannot be adequately addressed. The continuing disease progression may accelerate the loss of the initial PR benefit. With treatment available that slows the underlying disease progression, it is reasonable to evaluate whether the nintedanib impact on progression may enhance and extend PR benefits and its endurance over time.

Although nintedanib therapy reduces the annual rate of FVC decline by 50%, no consistent meaningful Health Related Quality of Life (HRQoL) effect was noted. Therefore the opportunity to improve HRQoL in patients with IPF remains an important unmet medical gap. Thus, the hypothesis is that combining nintedanib and PR will reduce the rate of FVC decline and improve or maintain patient functional performance and HRQoL

1.4 BENEFIT - RISK ASSESSMENT

This is not a pharmacologic interventional trial. All patients will be treated with nintedanib 150mg BID (twice daily) **for up to thirty months**. Patients will have been allowed to have dosage adjustment for management of adverse events but with resultant continuance of nintedanib therapy. They will not be allowed to have concurrent pirfenidone or N-acetyl cysteine (NAC) therapy but if treated with either drug previously they will need to complete a washout.

Although rare, a potential for **gastrointestinal perforation and** drug-induced liver injury (DILI) is under constant surveillance by sponsors and regulators. Therefore, this trial requires timely detection, evaluation, and follow-up of laboratory alterations in selected liver laboratory parameters to ensure patients' safety, see also [section 5.2.6](#), adverse events of special interest.

Pulmonary rehabilitation (PR) is a standard therapeutic component to the treatment of patients with chronic lung disease. All patients are assessed for their appropriateness for PR prior to initiation and during the course of PR. At any point in time that it is determined that the patient is no longer appropriate for PR, the program is discontinued.

2. TRIAL OBJECTIVES AND ENDPOINTS

2.1 MAIN OBJECTIVES, PRIMARY AND SECONDARY ENDPOINTS

2.1.1 Main objectives

The focus of this study is to assess the benefit of PR in IPF patients receiving stable nintedanib therapy (for up to 30 mos.) and to determine whether the PR benefit is maintained following cessation of PR. In addition, the “beyond the pill” or patient focused impact will be evaluated by measuring the effects of PR on patient activity levels and HRQoL. The enduring effect of these outcomes is important to the well-being of the patient. Conceptually nintedanib reductions in FVC decline may allow for an enduring effect following PR.

The main objectives of this study are:

[figure not shown]
- Determine the difference in change from baseline in 6MWD when pulmonary rehabilitation (PR) is added to stable underlying nintedanib therapy in patients with idiopathic pulmonary fibrosis (IPF)
- Determine the difference in change in QoL when pulmonary rehabilitation (PR) is added to stable underlying nintedanib therapy in patients with idiopathic pulmonary fibrosis (IPF)
- Determine if there is an enduring effect in 6MWD, QoL and lung function from pulmonary rehabilitation (PR) when pulmonary rehabilitation (PR) is added to stable underlying nintedanib therapy in patients with idiopathic pulmonary fibrosis (IPF)

2.1.2 Primary endpoint(s)

- Change from baseline in 6MWD at 12 weeks

2.1.3 Secondary endpoint(s)

- Change from baseline in QoL (SGRQ, KBILD, UCSD SOBQ) at 12 and 24 weeks
- Change from baseline in 6MWD at 24 weeks
- Change from baseline in lung function (FVC) at 12 weeks and 24 weeks using each of
 - Absolute change from baseline of FVC and FVC % predicted
 - Relative change from baseline of FVC and FVC % predicted
 - Absolute categorical change of FVC % predicted up to 12 and 24 weeks: decrease by >5%, increase by >5%, and change within ≤ 5
 - Absolute categorical change of FVC% predicted up to 12 and 24 weeks: decrease by >10, increase by >10, and change within ≤ 10
- Change from baseline in daily accelerometer activity at 12 and 24 weeks

3. DESCRIPTION OF DESIGN AND TRIAL POPULATION

3.1 OVERALL TRIAL DESIGN AND PLAN

This is a Phase IV, multi-centre, prospective, randomised, open label clinical trial to investigate the effect of pulmonary rehabilitation in patients with IPF currently treated with nintedanib at a dose of 150 mg bid for up to 30 months.

A total of approximately 290 patients with confirmed IPF diagnosis, already using nintedanib will be randomised, 145 in active arm and 145 in the control group. [REDACTED]

After a screening visit, if the patient complies with all inclusion and exclusion criteria and provides informed consent, randomisation will be performed by phone or Internet, using an Interactive phone/web Response System (IRT). Patients will then enter the treatment phase for 24 weeks. The treatment phase consists of 12 weeks of pulmonary rehabilitation for those patients randomized to that arm, to take place during the first 12 weeks of the treatment phase.

3.2 DISCUSSION OF TRIAL DESIGN, INCLUDING THE CHOICE OF CONTROL GROUP(S)

The use of pulmonary rehabilitation in IPF has been explored in small studies that have shown a positive outcome but without conclusive evidence of an enduring effect. It is believed that this is in part due to the underlying progressive disease not being addressed through active treatment. Consideration should therefore be given to the benefit of underlying antifibrotic therapy limiting the rate of lung function decline and allowing the effect of pulmonary rehabilitation to be more enduring.

The cohort in this study is patients that are treated with nintedanib for up to 30 months. This potentially addresses the concern that patients finish pulmonary rehabilitation and then return to a less active state because they are still left with an underlying chronic progressive disease. Given the findings in three pivotal studies that nintedanib slows the rate of decline in lung function ([c02098775-02](#), [c02155574-02](#)), this approach with this stable cohort may allow for a more enduring outcome from PR.

3.3 SELECTION OF TRIAL POPULATION

This trial will randomize 290 patients ([REDACTED] 145 [REDACTED] per treatment group at approximately 54 sites across the United States (US).

Screening of patients for this trial is competitive, i.e. screening for the trial will stop at all sites at the same time once a sufficient number of patients has been screened. Investigators

will be notified about screening completion and will then not be allowed to screen additional patients for this trial.

A log of all patients enrolled into the trial (i.e. who have signed informed consent) will be maintained in the investigator site file (ISF) at the investigational site.

Rescreening of patients who are previously screen failed for the trial is allowed within 1-2 weeks for patients that fail due to FVC, spirometry may be repeated once. Rescreening for administrative or other reasons must be discussed with the clinical monitor

3.3.1 Main diagnosis for trial entry

To qualify for the trial, patients must have a diagnosis of Idiopathic Pulmonary Fibrosis (IPF) according to American Thoracic Society (ATS), European Respiratory Society (ERS), Japanese Respiratory Society (JRS), and Latin American Thoracic Association (ALAT) criteria published in 2011, consistent with INPULSIS criteria. Patients must also have been treated with nintedanib 150 mg BID at a stable dose for **up to 30 months**.

Please refer to [section 8.3.1](#) (Source Documents) for the documentation requirements pertaining to the in- and exclusion criteria.

3.3.2 Inclusion criteria

1. Patients being treated with a stable dose of nintedanib 150 mg BID for up to 30 months. Patients who have recently started nintedanib 150 mg BID and have started by the day of randomization must be on nintedanib 150 mg BID a minimum of 10 days by the first day of pulmonary rehabilitation.
2. Age \geq 40 years at screening
3. Women of childbearing potential (WOCBP)¹ must be ready and able to use highly effective methods of birth control per ICH M3 (R2) ([R17-1399](#)) that result in a low failure rate of less than 1% per year when used consistently and correctly. A list of contraception methods meeting these criteria is provided in the patient consent form
4. Signed and dated written informed consent in accordance with ICH-GCP (International Council on Harmonization and Good Clinical Practice) and local legislation prior to admission to the trial
5. Confirmed diagnosis of IPF according to 2011 ATS/ERS/JRS/ALAT guidelines by lung biopsy or HRCT (based upon INPULSIS criteria ([c02098775-02](#), [c02155574-02](#)), (if biopsy only or HRCT done > 24 months prior to screening, a new HRCT to be done after consent and prior to or up to 7 days after Visit 2 for quantitative lung fibrosis score (QLF) for disease characterization)

¹ A woman is considered of childbearing potential (WOCBP), i.e. fertile, following menarche and until becoming post-menopausal unless permanently sterile.

Permanent sterilisation methods include hysterectomy, bilateral salpingectomy and bilateral oophorectomy. A postmenopausal state is defined as no menses for 12 months without an alternative medical cause.

6. Forced Vital Capacity (FVC) \geq 45% of predicted by the NHANES equation ([R04-1001](#)) or equivalent (after discussion with Clinical Monitor), historical within past 30 days can be used. Carbon monoxide Diffusion Capacity (DL_{CO}) (corrected for hemoglobin [Hgb]) 30-79% of predicted
7. FEV₁/FVC greater than/equal to .7
8. Physically capable of performing both a 6 minute walk test and [REDACTED], must successfully complete the practice tests for the 6 minute walk test, per the instructions [REDACTED]

3.3.3 Exclusion criteria

1. Major surgery (major according to the investigator's assessment) performed within 12 weeks prior to randomization or planned within 6 months after screening, e.g. hip replacement which could interfere with the ability to participate in pulmonary rehabilitation.
2. Any documented active or suspected malignancy or history of malignancy within 3 years prior to screening, except appropriately treated basal cell carcinoma of the skin or in situ carcinoma of uterine cervix
3. Patients who must or wish to continue the intake of restricted medications (see [Section 4.2.2.1](#)) or any drug considered likely to interfere with the safe conduct of the trial
4. Previous enrolment in this trial (except for rescreening as described in [Section 3.3](#))
5. Currently enrolled in another interventional investigational device or drug trial, or less than 30 days since ending another investigational device or drug trial(s), or receiving other investigational treatment(s)
6. Chronic alcohol or drug abuse or any condition that, in the investigator's opinion, makes them an unreliable trial patient or unlikely to complete the trial
7. Women who are pregnant, nursing, or who plan to become pregnant in the trial
8. Previous participation in pulmonary rehabilitation program within 45 days prior to signing consent

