Main in- and exclusion criteria	
 Age \geq 40 years. Forced Vital Capacity (FVC) \geq 45% of predicted

	
 • FEV₁/FVC greater than/equal to .7 and Carbon Monoxide Diffusion Capacity (DL_{CO}) (corrected for hemoglobin [Hgb]) 30-79% of predicted • Confirmed diagnosis of IPF according to 2011 ATS/ERS/JRS/ALAT guidelines by High Resolution Computed Tomography (HRCT) (consistent with INPULSIS criteria) or lung biopsy taken within 24 months prior to providing Informed Consent • Treated on a stable dose of nintedanib for up to 30 months. Patients who have recently started nintedanib 150 mg BID and have started by the day of randomization must be on nintedanib 150 mg BID a minimum of 10 days by the first day of pulmonary rehabilitation. 
Exclusion
 
 • Major surgery within 12 weeks prior to randomization or planned within 6 months after screening which could interfere with the ability to participate in pulmonary rehabilitation • Active or suspected malignancy or history of malignancy within 3 years prior to screening • Currently enrolled in or less than 30 days since ending another interventional investigational device or drug trial • Women who are pregnant, nursing, or who plan to become pregnant in the trial • Previous participation in pulmonary rehabilitation program within 45 days prior to signing informed consent
Test product(s):	nintedanib
dose:	150 mg BID
mode of administration:	oral
Comparator products:	None
dose:	NA
mode of administration:	NA
Duration of treatment:	24 weeks
Endpoints	
 • Primary Endpoint 
 ○ Change from baseline in 6MWD at 12 weeks • Secondary Endpoints 
 ○ Change from baseline in QoL (SGRQ, KBILD, UCSD SOBQ) at 12 and 24 weeks ○ Change from baseline in 6MWD at 24 weeks ○ Change from baseline in lung function (FVC) at 12 weeks and 24 weeks using each of

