	
 • Absolute change from baseline of FVC and FVC % predicted • Relative change from baseline of FVC and FVC % predicted • Absolute categorical change of FVC % predicted up to 12 and 24 weeks: decrease by >5%, increase by >5%, and change within ≤ 5 • Absolute categorical change of FVC% predicted up to 12 and 24 weeks: decrease by >10, increase by >10, and change within ≤ 10 
○ Change from baseline in daily accelerometer activity from baseline at 12 and 24 weeks
 
[REDACTED]

Safety criteria:
	
 • Vital signs, physical examination, weight • Clinical laboratory tests (haematology, clinical chemistry, and urinalysis) • Reporting of adverse events • 12 lead electrocardiogram

Statistical methods:
	
The primary (6MWD at 12 weeks) will be analysed using the Analysis of Covariance model including intervention as a fixed categorical covariate and baseline 6MWD as continuous covariate
 
6MWD will be analysed on the original scale. [REDACTED]
 
[REDACTED] all other assessments will be analysed using original scales.

	
For secondary [REDACTED] endpoints, 12-week endpoints will be analysed using similar ANCOVA methodology as the primary endpoint. The 24-week endpoints will be analyzed using a mixed model with repeated measures.
 
Descriptive statistics will be shown for all efficacy and safety endpoints.

--	---

FLOW CHART

	Screening		Interventional Period					
	0	1	Treatment					
Visit	0	1	2	3	4	5	6	7 (EOT)
Weeks of treatment	-2	-1	0	3	6	12	18	24 ⁶
Day	At least 7 days before visit 1	≥ 7d before V 2	1	22	43	85	127	169
Time window				±3	±3	±3	±3	±7
Informed consent	X*							
Demographics/ baseline conditions		X						
Medical history		X						
In-/exclusion criteria	X	X	X					
Physical examination ⁷ , vital signs		X	X	X	X	X	X	X
Laboratory test		X	X	X	X	X	X	X
Pregnancy test		X	X	X	X	X	X	X
Spirometry (FVC)		X	X			X		X
SpO ₂ (peripheral capillary oxygen saturation)		X	X			X		X
DL _{CO}		X	X			X		X
HRCT sent for outcomes review ¹		X ¹	X ¹					
12-lead electrocardiogram (ECG)		X						X
(Practice) Six-minute walk test		X						
Six minute walk test			X			X		X
		■	■			■		■
Instruct Patient on Activity Monitoring and PROactive tool (eDiary) ²	X	X	X		X		X	
Activity Monitoring (Dynaport)	X	X	X			X		X
SGRQ, KBILD, UCSD SOBQ		X	X			X		X
PROactive Tool ^{2,3}	X	X	X			X		X
Randomisation			X					
Schedule pulmonary rehab days for assigned patients ⁶			X					

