5.1.2 Assessment of efficacy

5.1.2.1 6 Minute walk test

The distance measured in the 6 Minute Walk Test at 12 and 24 weeks will be assessed according to the procedures described in [Appendix 10.1](#).

Four 6 MWTs will be performed during the trial (one practice and three tests). At Visit 1 a practice 6 MWT, also referred to as the Titration Walk Test, will be conducted to acquaint the patient with the procedure and to determine the level of oxygen needed for subsequent testing. As per inclusion criterion #8, patients must be physically able to perform a 6MWT, as per the instructions. Patients who cannot complete the Titration Walk Test will be considered a Screen Failure. Three 6 MWTs will be conducted during the randomized treatment phase at Visits 2 (baseline), 5 and 7 (End of Treatment). During the 6 MWT, the Borg Scale will be administered. Detailed instructions for the conduct of the 6 MWT and Borg Scale are provided in the ISF and Appendix 10.1 and [10.2](#) and in the distributed instructional video. It is important the instructions are followed exactly. The test will be performed at approximately the same time each day from time of Visit 2 testing. Patients who cannot complete the 6MWT after randomization will remain in the trial.

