6. INVESTIGATIONAL PLAN

6.1 VISIT SCHEDULE

This trial consists of two parts, a screening and an interventional period. The screening period consists of the time between signing consent and randomization, and will last a minimum of 7 days. The interventional period consists of the time from randomization through the week 24 assessment visit.

There are two screening visits (Visit 1, which must be preceded by a separate informed consent Visit 0) and 6 visits (Visits 2 to 7) planned within the 24 week interventional period. There is no follow up period in this trial.

After giving his/her informed consent, the patient will be screened for inclusion (see [Section 3.3.2](#) and exclusion criteria (see [Section 3.3.3](#)) for the trial at Visits 0, 1 and Visit 2 (refer to [Flowchart](#)).

The patient will be dispensed an activity monitor and ProActive tool (eDiary) at the consent visit, and will wear the activity monitor and use the eDiary for 7 days prior to Visit 1 for training purposes.

Visit 2 can be performed once the results from local laboratory of Visit 1 are obtained and the patient has worn the activity monitor and completed the eDiary for 7 days. If for any reason the screening phase for an individual patient lasts for more than 6 weeks, then the laboratory examination for Visit 1 has to be repeated before randomization. The patient will be randomized at Visit 2 if all inclusion and none of the exclusion criteria are fulfilled. Central HCRT is not required prior to randomization, but if historical HRCT is not available to be sent for central calculation of QLF, a scan should be obtained after screening/consent at the latest 7 days after Visit 2.

On treatment visits will be performed at 3, 6, 12, 18 and 24 weeks. Procedures for these visits are outlined in the flow chart and detailed instructions are available in [Section 5](#), select appendices and the ISF, as applicable.

Visit 7 is the end of treatment visit, there is no follow up period. Visit 7 procedures should be followed for early termination visits if possible.

If a patient misses a visit, the visit should be rescheduled as soon as possible. If unable to reschedule, the clinical monitor should be contacted.

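### Exclusion 8 ends its look-back at consent, so rehabilitation begun between consent and the Visit 2 baseline walk breaks no criterion; the likely effect is a small dilution

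*Protocol*

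**What the plan says.** Exclusion 8 in Protocol 3.3.3 reads "Previous participation in pulmonary rehabilitation program within 45 days prior to signing consent", and the synopsis has the same rule: "Previous participation in pulmonary rehabilitation program within 45 days prior to signing informed consent". Both count back from consent.

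The baseline comes later. Protocol 5.1.2.1 states "Three 6 MWTs will be conducted during the randomized treatment phase at Visits 2 (baseline), 5 and 7", and randomisation is also at Visit 2. The flow chart places consent (Visit 0) "At least 7 days before visit 1", and Visit 1 at least 7 days before Visit 2. Section 6.1 says instead that screening "will last a minimum of 7 days". It sets no maximum: "If for any reason the screening phase for an individual patient lasts for more than 6 weeks", the only consequence is that the Visit 1 laboratory examination is repeated.

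Exclusion 1, in the same list, uses a different anchor: major surgery "performed within 12 weeks prior to randomization".

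Section 1.4 says of the test intervention: "Pulmonary rehabilitation (PR) is a standard therapeutic component to the treatment of patients with chronic lung disease".

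**The concern.** Rehabilitation is the only randomised difference in this trial, and the primary endpoint is the change from the Visit 2 walk. A look-back on earlier rehabilitation helps to keep its residual benefit out of that baseline. To do so fully, it has to run up to the baseline measurement. As written, it stops at least one and probably two or more weeks short.

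The result is uneven. A patient whose programme ended 44 days before consent is excluded. A patient who starts a programme the day after consent and is still attending in the week of the baseline walk is not. Because the protocol regards rehabilitation as ordinary care for chronic lung disease, referral by a treating physician during screening is conceivable.

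An affected patient assigned to rehabilitation has somewhat less left to gain. An affected patient assigned to control either keeps the early gain, which narrows the difference between arms, or loses it, which partly or fully offsets the narrowing. The stake is therefore mainly a diluted treatment difference.

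**Working it through.** **Does any other rule close the interval?**

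- Protocol 4.2.2.1 restricts medications only.
- Eligibility is checked again at Visit 2 (flow chart, 6.1 and 6.2.2), but the wording checked still ends at consent.
- SAP 6.2, deviation C1, is defined by the assigned arm: rehabilitation not prescribed in the rehabilitation arm, or prescribed in the standard-care arm. It does not address what happened during screening.
- Rehabilitation attendance is recorded from Visit 3 onwards and only for the rehabilitation arm (6.2.2).
- Concomitant treatments are recorded from consent (flow chart footnote), which may capture outside rehabilitation. However, the SAP 7.2.2 paragraph on summarising non-drug therapies is struck through.

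Nothing found makes such a patient ineligible.

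**Length of the interval.** By the flow chart, 7 + 7 = 14 days at least. By Section 6.1, 7 days at least. There is no cap, and more than 6 weeks is expressly foreseen.

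**The plan's own figure.** Inputs from Protocol 7.7: difference 30 m, SD 85 m, 80% power, two-sided 0.05.

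n per arm = 2 × (1.960 + 0.842)² × 85² / 30² = 126.02, rounded up to 127, or 254 in total. This matches the protocol. The exact t-test calculation also gives 127. The standard error of the difference is 85 × √(2/127) = 10.7 m.

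**Illustration of size.** The documents give neither the gain from a partial course nor the share of patients affected, so both are assumed:

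1. The 44.3 m cited in 7.7 accrues linearly over 12 weeks.
2. A fraction f of each arm is exposed during screening.
3. Exposed controls keep the gain, and exposed rehabilitation patients finish where they otherwise would.

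Gain per affected patient: g = 44.3 × weeks / 12.

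- Two weeks: 44.3 × 2/12 = 7.4 m
- Six weeks: 44.3 × 6/12 = 22.15 m

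Reduction of the mean difference = f × g:

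| f | Two weeks | Six weeks |
|---|---|---|
| 2% | 0.15 m | 0.44 m |
| 5% | 0.37 m | 1.11 m |
| 10% | 0.74 m | 2.22 m |

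At f = 5% the 30 m difference becomes 29.6 m (two weeks) or 28.9 m (six weeks). With 127 per arm, power would be 79% or 77%. At f = 10% the differences are 29.3 m and 27.8 m, with power 78% and 74%.

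If exposed controls instead lose the whole early gain, their change falls by g as well and the reduction is cancelled. The table is therefore the no-fading case.

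**The case against.** The strongest reply is that the gap is narrow. A patient already in rehabilitation at consent, or within 45 days before it, is caught. Only someone who agrees to join a rehabilitation trial and then starts a programme elsewhere before Visit 2 slips through. Section 1.4 shows that this is possible, not that it happens. The nominal schedule allows two weeks. At two or three sessions a week for 12 weeks (4.1.1), that is 4 to 6 of 24 to 36 sessions, one sixth of a course. Screening beyond six weeks is a contingency. All of this stands, and it is why the estimated effect is small.

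Second, affected patients would be expected in both arms under 1:1 randomisation, and baseline distance is a covariate in the planned ANCOVA (7.3.1). That argues against a systematic baseline imbalance and against a spurious benefit. It does not remove dilution, because baseline distance does not identify who has already been trained.

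Third, C1 carries no date limit and goes to medical review, so a control patient still in rehabilitation after randomisation might be noticed. An exposed patient in the rehabilitation arm would not be.

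Fourth, SAP Section 4 reports termination and limits the primary and secondary endpoints to descriptive outcomes. No primary test remains to lose power, though the descriptive difference still has to be interpreted.

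**Conclusion.** The gap in the wording is real, and the point is minor. Rehabilitation started or restarted after consent and before Visit 2 breaks no criterion, and it may leave the baseline walk partly raised. Under the linear-accrual assumption, the likely consequence is a dilution of about 0.4 to 1.1 m if 5% of patients are affected, and 0.1 to 2.2 m over 2% to 10%. The standard error is about 10.7 m. Screening longer than six weeks would give larger values, and fading in controls would give smaller ones.

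A reader might infer more than this: that such patients have a baseline already raised by a full treatment effect, that the whole 30 m or 44.3 m is at stake for each of them, or that the 12-week change no longer measures the effect of starting rehabilitation. The documents do not support these readings. Both figures describe a full effect, no partial-course gain is given, just-completed courses are excluded, and no prevalence is stated.

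Separately, the flow chart's 7 + 7 days and the 7-day minimum in Section 6.1 disagree and must be reconciled.

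**What to change.** Reword exclusion 8 in 3.3.3 and in the synopsis to: *Participation in a pulmonary rehabilitation program at any time from 45 days before signing consent until randomisation.* Apply it at the eligibility check that already takes place at Visit 2. This brings the end of the window into line with the anchor used in exclusion 1.

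The cost is one line in an amendment and in the eligibility checklist, plus a few extra screen failures. The sample size is unchanged (254, or 282 with dropout).

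For patients already enrolled in the terminated trial, the sponsor can instead search the recorded concomitant treatments for rehabilitation between consent and Visit 2 and report the count by arm in the abbreviated trial report. The report should say that such treatment may not have been captured completely.
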